6.4. Analysis of Immunogenicity

Anti-L-ASNase antibodies will be assessed in the safety population. Results will be described by:

Sponsor:	NOPHO – Nordic Society of Pediatric Hematology & Oncology		
Protocol:	NOR-GRASPALL 2016		
Document Version No.:	2.0	Document Date:	14-May-2021

- Frequency tables of anti-L-ASNase antibody status (positive/negative) for Screening, Confirmatory and Neutralizing activity
- Frequency tables of antibody status at each time point of assessment.
- Summary statistics: Change in antibody status: proportion of patients with sero-conversion (negative to positive), and median time to sero-conversion

6.5. Analysis of Exploratory Endpoints

NA

Sponsor:	NOPHO – Nordic Society of Pediatric Hematology & Oncology		
Protocol:	NOR-GRASPALL 2016		
Document Version No.:	2.0	Document Date:	14-May-2021

7. DRUG EXPOSURE

Study duration will be derived in weeks, and defined as the number of days between the randomization and the last known study visit; i.e., (date of last visit - date of treatment +1)/7.

Analysis of all exposure to study drug will be based on the safety population. The number of doses of eryaspase planned for a respective patient depended on the phase in the treatment course to receive asparaginase. However, the overall exposure to study drug, the number of patients completing the planned doses of asparaginase, and the dose intensity will be summarized using descriptive statistics.

7.1. Dose Intensity

The dose intensity will be computed as (total actual dose received)/ (total remaining asparaginase dose expected) x 100. Visits with a non-missing planned dose and an actual dose that is zero or missing are counted as dose intensity of 0%.

7.2. Treatment Duration

Total treatment duration for eryaspase will be summarized. The duration of treatment will be defined as follows:

Eryaspase administered every 2 weeks (Day 1 and Day 15) at a dose of 150 U/kg.

Administrations will continue until the intended doses of asparaginase are completed.

Eryaspase can be reduced at the discretion of the Investigator in the event of toxicities occurring that are related to the treatment.

For eryaspase, treatment duration in months will be defined as:

(last injection date – first injection date +1) / 30.4375.

7.3. Compliance

The overall compliance (%) will be defined as: number of infusions received/number of infusions planned

Based on the definitions above, the following summary tables will be provided for eryaspase:

- Study duration (months): summary statistics,
- Treatment duration (months): summary statistics,

Sponsor:	NOPHO – Nordic Society of Pediatric Hematology & Oncology		
Protocol:	NOR-GRASPALL 2016		
Document Version No.:	2.0	Document Date:	14-May-2021

- Compliance: summary statistics and frequency table for the categories <60%, 60% to <80%, 80% to 100%, >100%.

Sponsor:	NOPHO – Nordic Society of Pediatric Hematology & Oncology		
Protocol:	NOR-GRASPALL 2016		
Document Version No.:	2.0	Document Date:	14-May-2021

8. SAFETY AND TOLERABILITY ANALYSES

All safety summaries and analyses will be based upon the safety population, which includes all patients who received at least one dose of study drug.

The analysis of safety and tolerability data includes an overall summary of tolerability, AEs (incidence, intensity, seriousness, and relationship of AEs to the study drug), drug exposure (duration of treatment), dosing information/compliance, concomitant medications, clinical laboratory results, ECG findings, and Karnofsky/Lansky PS.

8.1. Adverse events

Tables summarizing the number of subjects with AEs leading to death, SAEs, or prematurely discontinued the study due to an AE, will be presented.

The primary presentation of AE data will be prepared without regard to causality or relationship to study drug. Adverse event verbatim terms are coded by the MedDRA coding system and displayed in tables and data listings using SOC and PT. The NCI CTCAE will be used to grade the severity of AEs. For AEs not included in the NCI CTCAE, categorization by mild (Grade 1), moderate (Grade 2), severe (Grade 3), life threatening (Grade 4), or death (Grade 5) will be used.

AEs will be coded using the MedDRA version 21.0. In an overall AE summary table, the incidence of treatment-related TEAEs will be summarized by System Organ Class (SOC) and Preferred Term (PT) (in alphabetic order) for patients experiencing at least one:

- The number and percentage of patients with any treatment-emergent AE (TEAE).
- The number and percentage of patients with any TEAE assessed by the investigator as related to treatment.
- The number and percentage of patients with any treatment-emergent serious AE (SAE).
- The number and percentage of patients with any related serious TEAE.
- The number and percentage of patients with TEAEs by maximum intensity based on CTCAE grade.
- The number and percentage of patients with Grade 3 or 4 TEAE.
- The number and percentage of patients with related Grade 3 or 4 TEAE.
- The number and percentage of patients with any treatment-emergent AE by severity. The NCI CTCAE (version 5.0) will be used to grade the severity of AEs. For AEs not

Sponsor:	NOPHO – Nordic Society of Pediatric Hematology & Oncology		
Protocol:	NOR-GRASPALL 2016		
Document Version No.:	2.0	Document Date:	14-May-2021

included in the NCI CTCAE, categorization by mild (Grade 1), moderate (Grade 2), severe (Grade 3), life threatening (Grade 4), or death (Grade 5) will be used.

- The number and percentage of patients with any treatment-emergent AE resulting in treatment discontinuation.
- The number and percentage of patients with any treatment-emergent AE with an outcome of death (fatal outcome).

In general, inferential statistical tests are not performed for AE incidence rates.

Adverse events of similar nature will be grouped together for better characterization of the adverse events, including:

- Transaminases increased: ALT increased, AST increased, and Transaminases increased.
- Anemia: Anemia, hemoglobin decreased
- Thrombocytopenia: Thrombocytopenia, platelet count decreased
- Leukopenia: Leukopenia, white blood cells count decreased
- Leukocytosis: Leukocytosis, white blood cells count increased
- Hyperglycemia/Diabetes: Hyperglycemia, Diabetes mellitus, Diabetes mellitus inadequate control, Type 2 diabetes mellitus, blood glucose level increased
- Hypertriglyceridemia: Hypertriglyceridemia, triglycerides increased
- Hepatotoxicity: Liver injury, drug-induced liver injury, hepatocellular injury, Venoocclusive liver disease
- Hyperuricemia: Hyperuricemia, blood uric acid increased
- Hypokalemia: Blood potassium decreased, hypokalemia
- Hyponatremia: Blood sodium decreased, hyponatremia
- Hypocalcemia: Blood calcium decreased, hypocalcemia
- Pancreatitis: Pancreatitis, Acute pancreatitis
- Biochemical pancreatitis: Lipase increased, Amylase increased, pancreatic enzymes increased
- Drug hypersensitivity reaction: Drug hypersensitivity, hypersensitivity, anaphylactic reaction, anaphylactic shock, erythema multiform, edema, dermatitis allergic, face edema
- 4. Other allergic reaction: Rash, Erythema multiform, Food allergy, Anaphylactic shock, Transfusion reactions, Angioedema, allergic transfusion reaction.

All AEs and SAEs will be collected and reported in the patient's eCRF throughout study duration (i.e. for time subject signs the informed consent and until 30 days after last administration of eryaspase or chemotherapy. All AEs along with the coded terms will be listed.

The following general rules apply to adverse events:

Sponsor:	NOPHO – Nordic Society of Pediatric Hematology & Oncology		
Protocol:	NOR-GRASPALL 2016		
Document Version No.:	2.0	Document Date:	14-May-2021

- TEAEs are defined as those AEs that started on or after the first dose of study medication or that worsened after the first dose of study medication and with an onset date occurring during the treatment period.
- Treatment period is defined from the first dosing day of study treatment (minimum of the first dosing day for eryaspase (Day 1) until 30 days after last dose of study treatment (maximum of the last dosing day for eryaspase). This includes the safety follow-up period as well.
- If an AE is reported for a given patient more than once during treatment, the worst severity and the worst relationship to study treatment will be tabulated.
- In table summaries, patients will be counted only once at the PT level if multiple incidences of the same event occur within a SOC. Patients will be counted only once at the SOC level if multiple events occur within that SOC. For example, a patient who experiences an event of anemia and an event of neutropenia will be counted twice at the PT level (anemia, neutropenia) and once at the SOC level (vascular disorders).
- Investigator-assessed causality and relationship to study drugs will also be presented.
- In case a subject had AEs with missing and non-missing grades, the maximum of the non-missing grades will be displayed.

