3.2 Secondary Objectives

- To assess the immunogenicity of eryaspase as determined by assessment of anti-L-asparaginase antibodies and neutralizing antibodies.
- To assess the overall safety and tolerability of eryaspase in combination with multi-agent NOPHO ALL 2008 chemotherapy according to the PdL toxicity consensus definitions for asparaginase related toxicities (hypersensitivity, pancreatitis, hyperlipidemia, SOS, thrombosis, osteonecrosis, and fungal infections)(25).
- Evaluate the effect of Eryaspase on the concurrent maintenance therapy with 6-mercaptopurine and methotrexate. Levels of cytotoxic methotrexate (MTX polyglutamates) and 6-mercaptopurine metabolites (6-thioguanine nucleotides, 6TGN, and methylated metabolites, MeMP) and of DNA-TGN levels in circulating leukocytes.

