4.2 Secondary Endpoints

The secondary endpoints are to evaluate:

- The safety and tolerability of eryaspase in combination with standard multi-agent NOPHO ALL 2008 or ALLTogether pilot protocol chemotherapy assessed during eryaspase treatment period according to potential toxicities defined in the Adverse Experience section.
- Toxicity of the eryaspase treatment compared to the conventional PEG-asparaginase treatment. Toxicity and SAE's will be evaluated according to the PdL toxicity consensus definitions.
- Levels of maintenance metabolites

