5.3 Inclusion Criteria

A patient is eligible for the study if all of the following criteria are met:

1. Male or female aged 1-45 years at diagnosis of ALL
2. First line non-high risk (HR) ALL patients enrolled in NOPHO ALL 2008 or ALLTogether pilot protocol including PEG-asparaginase regimen

3. Documented hypersensitivity reaction to PEG-asparaginase with either:
 - Clinical allergy to PEG-Asparaginase (mild/severe) OR
 - Serum asparaginase activity below the lower level of quantification
4. Karnofsky/Lansky score ≥ 50 .
5. Ability to understand, and willingness to sign, a written informed consent document and to comply with the scheduled visits, treatment plans, laboratory tests, and other study procedures. For patients under 18 years of age, either both parents or the legally appointed representatives will need to provide consent.

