10.2 AEs/SAEs not to be reported

When treating children with cancer, the strategy is generally to treat to the limit of toxicity. Thus, all patients will be at a significant risk of experiencing AE's and SAEs, and all patients and families are informed hereof, when they enter therapy. Most patients will experience febrile neutropenia with or without confirmed bacteraemia, and these are potentially life threatening or may require inpatient hospitalization or prolongation of existing hospitalization. Thus, these AE's and several other SAEs reflect the overall treatment intensity of the current protocols for childhood ALL and not only the

treatment of asparaginase. In addition, treating to neutropenia is in principle the goal of several of the treatment phases and will frequently lead to infections (febrile neutropenia and other infections).

A number of toxicities are so well-known and frequent during therapy that they will not be reported. These includes:

- Since leukopenia is the target toxicity (monitoring parameter), this side-effect will not be regarded as a SAE. This also includes febrile neutropenia leading to hospitalization or prolongation of ongoing hospitalization if the patient's condition otherwise is good with no signs of septic shock.
- Since thrombocytopenia is the target toxicity (monitoring parameter) this side-effect will not be regarded as a SAE.
- A rise in aminotransferases with normal liver function tests (i.e. bilirubin and INR (or coagulation factor 2-7-10) is a well-known side effect of HD-MTX, 6MP and asparaginase and will not be regarded as a SAE.
- A rise in bilirubin to less than 5x UNL.
- Hyperglycemia will not be reported.
- Infection/fever leading to hospitalisation or prolongation of existing hospitalisation.

The overall safety and tolerability of eryaspase in combination with multi-agent NOPHO ALL 2008 or ALLTogether pilot protocol chemotherapy will be evaluated according to the PdL toxicity consensus definitions for asparaginase related toxicities (hypersensitivity, pancreatitis, hyperlipidemia, SOS, thrombosis, osteonecrosis, and fungal infections)(1). Table 3 contains the toxicities potentially related to treatment with asparaginase. All of these toxicities must be reported to PI's and on the CRF.

TABLE 3. POTENTIAL RELATED TOXICITY TO ASPARAGINASE (1)

Toxicity	Consensus definition

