6.2.3. Sensitivity, Covariate and Subgroup Analyses

The ASNase concentration on Day 14 following the first and fourth infusion for each patient will be linearly dose adjusted from 150 U/kg to 100 U/kg and the proportion of patients with values >100 U/L determined.

The primary endpoint and key secondary endpoint will be evaluated in the subgroups listed below with data presented in Forest Plots (point estimates and 95% confidence intervals) for each endpoint together with the effect in the overall evaluable patients' population. The purpose of this evaluation is to assess the homogeneity of treatment effect.

Sponsor:	NOPHO – Nordic Society of Pediatric Hematology & Oncology		
Protocol:	NOR-GRASPALL 2016		
Document Version No.:	2.0	Document Date:	14-May-2021

Subgroups to be used:

- Gender
- Age (<18 years, \geq 18 years)
- for age <18: <11 years, 11- <18
- Antibody status at baseline (neutralizing activity as positive vs negative)
- Grade of allergic reactions to Oncaspar (Grade 1 and 2 combined vs Grade 3 and Grade 4 combined)
- Silent inactivation to Oncaspar (Yes, No)

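### SAP 8.1 grades and groups adverse events by rules other than the PdL consensus definitions that the protocol sets for asparaginase toxicity, and does not declare the departure

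*SAP*

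**What the plan says.** **Protocol.** The secondary safety objective (3.2) is assessed "according to the PdL toxicity consensus definitions for asparaginase related toxicities". The secondary endpoint (4.2) repeats this: "Toxicity and SAE's will be evaluated according to the PdL toxicity consensus definitions". It also asks for eryaspase toxicity to be set against conventional PEG-asparaginase. Section 10.2 lists the "asparaginase related toxicities (hypersensitivity, pancreatitis, hyperlipidemia, SOS, thrombosis, osteonecrosis, and fungal infections". It adds that "Table 3 contains the toxicities potentially related to treatment with asparaginase" and makes these toxicities mandatory on the CRF. Table 3 gives each entry its own definition and, apart from silent inactivation, its own grades.

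**SAP.** Section 4.3 fixes CTCAE version 5.0. Section 8.1 says "The NCI CTCAE will be used to grade the severity of AEs" and supplies a generic scale from mild (1) to death (5) for events that CTCAE does not cover. Events are tabulated by MedDRA system organ class (SOC) and preferred term (PT). A list of term groups is then added, introduced as examples. One is Hepatotoxicity, made up of "Liver injury, drug-induced liver injury, hepatocellular injury" and veno-occlusive liver disease. PdL and the consensus definitions are not mentioned in the SAP text.

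**Prior allergy.** SAP 6.2.3 has a subgroup on "Grade of allergic reactions to Oncaspar", grades 1 and 2 against grades 3 and 4. SAP 5.2.2 tabulates prior allergy in four grades. The inclusion criterion in Protocol 5.3 reads "Clinical allergy to PEG-Asparaginase (mild/severe) OR".

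**The concern.** This is more than missing detail. The SAP states a grading rule and a grouping rule that conflict with the standard the protocol chose for this endpoint. A programmer who follows the SAP would produce CTCAE-graded preferred-term tables and some grouped rows, none of which is a PdL toxicity.

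Two things are at stake. First, a reader who wants the proportion of patients with, say, thromboembolism or SOS by the protocol's definition would have to assemble it from single preferred terms, and could not recover the PdL grade. Second, the comparison with PEG-asparaginase in Protocol 4.2 is in PdL terms, so eryaspase figures on another scale cannot be set beside it directly.

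**Working it through.** The plan has no figure to reproduce on this point. The check sets the protocol's seven toxicities against the groups in SAP 8.1.

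| Toxicity (Protocol 3.2, 10.2) | PdL in Protocol Table 3 | SAP 8.1 group |
|---|---|---|
| Hypersensitivity | One entity; includes rash, oedema/angioedema and anaphylaxis; 2 grades | Split over two groups |
| Pancreatitis | Two of three features; mild or severe by a 72-hour limit or complications; death | Two groups of coded terms |
| Hyperlipidemia | Triglycerides and cholesterol; 3 grades | Triglycerides only |
| SOS | Three of five criteria; 4 grades | Inside Hepatotoxicity |
| Thrombosis | Grades 1 to 5, grade 2 split into 2A and 2B | None listed |
| Osteonecrosis | MRI-confirmed; 4 grades | None listed |
| Fungal infection | No row in Table 3 as supplied | None listed |

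**Count.** 3 without a group + 1 pooled + 1 partly covered + 2 grouped on other definitions = 7. None of the seven is summarised on PdL grades.

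**The two allergy groups.** Drug hypersensitivity reaction includes edema and face edema. Other allergic reaction holds rash and angioedema, together with food allergy and transfusion reactions. Signs of the single PdL entity are therefore divided, and some are mixed with events that are not asparaginase hypersensitivity. Anaphylactic shock and erythema multiforme are listed in both groups, so one event would be counted in two rows.

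**Declared changes.** The SAP revision history lists the analyses deleted because data were not available; PdL toxicity is not among them. Section 9 discusses only the re-designation of the primary and secondary endpoints.

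**Scale of the reporting effect (illustration, not a forecast).** Assume a safety population of 55, the SAP 4.1 recruitment target, and four patients with four different thrombosis terms. The preferred-term table shows four rows of 1/55 = 1.8%. A thrombosis row would show 4/55 = 7.3%. The Wilson 95% interval, with z² = 3.8416, is:

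- centre: (4/55 + 3.8416/110) / (1 + 3.8416/55) = 0.1076/1.0698 = 0.1006
- half-width: 1.96 × √(0.0727 × 0.9273/55 + 3.8416/(4 × 55²)) / 1.0698 = 0.0770/1.0698 = 0.0720
- interval: 2.9% to 17.3%

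With no events, a preferred-term table has no row at all. A toxicity table would state 0/55 with upper limit z²/(n + z²) = 3.8416/58.8416 = 6.5%. With the protocol's 50 patients the limit is 3.8416/53.8416 = 7.1%.

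**Prior-allergy subgroup.** Table 3 numbers hypersensitivity 1 (mild) and 2 (severe). On that scale the grade 1–2 arm holds every graded patient and the grade 3–4 arm holds none. On the four grades of SAP 5.2.2 either arm can be filled. The documents do not say which scale the eCRF records.

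**The case against.** The strongest defence is that nothing is lost. The SAP tabulates events by SOC and PT and lists all events with their coded terms, so thrombosis, osteonecrosis, fungal infection and veno-occlusive disease all remain visible. The group list is open, and the output shells are in a separate document that was not supplied. Protocol 12.3 itself asks only for MedDRA-coded events with patient counts, rates, severity and relationship, which SAP 8.1 delivers. PdL definitions could also be applied by the investigator when the CRF is completed.

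Most of this stands, and it limits the point. A reader might infer that the secondary safety endpoint disappears; the documents do not support that, because the events are collected and displayed. A reader might also infer that SOS cannot be told apart from raised liver enzymes. That is wrong: transaminases have their own group, and veno-occlusive disease keeps its preferred-term row. Only the Hepatotoxicity group pools it, and only with liver-injury terms.

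The defence does not supply the PdL summary. SOC rows count each patient once, but together with patients who had any other event in that class. An open list does not tell the programmer to build a PdL row, and the SAP names a different grading scale outright.

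It is also tempting to call the grade 3–4 allergy subgroup empty. That follows only if the eCRF uses the protocol's mild/severe scale, and the SAP's own four-grade table points the other way. The subgroup concerns the activity endpoints, not eryaspase toxicity, so it is a separate matter of clarification.

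**Conclusion.** The point holds as an undeclared conflict between protocol and SAP. The protocol sets PdL definitions and grades for asparaginase toxicity; the SAP sets CTCAE, a generic fallback scale and term groups that do not match PdL. Three of the seven named toxicities have no listed group, one is pooled, one is partly covered, and two are grouped on other definitions. What is missing is a patient-level, PdL-graded incidence for each toxicity; the underlying events are not missing. The primary and key secondary tests are unaffected.

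This should be corrected before the safety tables are final. The conclusion rests on the SAP text alone, since the output shells and eCRF were not available. The statement about SOS further assumes that veno-occlusive liver disease is its coded term, which neither document says. The allergy-subgroup remark is conditional on the eCRF scale.

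**What to change.** - Add one table to SAP 8.1, on the safety population: number, percentage and Wilson 95% interval by PdL grade for each toxicity defined in Protocol Table 3, taken from the CRF toxicity record. Give SOS its own row and include cholesterol under hyperlipidemia. Silent inactivation has no grades in Table 3, so report its incidence only.
- Report fungal infection as number and percentage with interval. Take its PdL definition from the consensus paper that the protocol cites, because Table 3 as supplied has no row for it.
- Keep the CTCAE tables. If a departure from PdL is intended, declare it in Section 9 with the reason.
- State in SAP 5.2.2 and 6.2.3 which scale the eCRF uses for prior PEG-asparaginase allergy. If it is the protocol's scale, define the subgroup as mild versus severe; if it is a four-grade scale, name it and keep the split.

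**Cost.** One table and one clarified subgroup line. The Table 3 toxicities are already required on the CRF; fungal infection needs its definition added and a check that it was recorded. The downside is two grading scales in one report, which a footnote can explain.

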8.2. Laboratory Data

Clinical laboratory values will be expressed using SI units. Local laboratories are being used for this clinical study for hematology and blood chemistry. For each individual laboratory used, laboratory reference ranges and units are collected. Reference ranges will be entered into the local laboratory normal range.

The laboratory collection CRFs (hematology and serum chemistry) include fields for additional, non-protocol-required clinically significant laboratory tests, including laboratory test name, result, units, normal range low, and normal range high.

NCI CTCAE version 5 will be used for grading applicable laboratory tests.

Standard biological assessments will be performed at the local laboratory of the Investigator's site at selection, before any eryaspase administration as follows:

- Hematology: complete blood count (CBC);
- Serum Biochemistry: lactate dehydrogenase (LDH), bilirubin, alanine aminotransferase (ALT), aspartate transaminase (AST), gamma glutamyl transpeptidase (GGT), alkaline phosphatase (ALP), albumin, potassium and calcium;
- Coagulation: fibrinogen, antithrombin III (ATIII), partial thromboplastin time (PTT), and prothrombin time.

Sponsor:	NOPHO – Nordic Society of Pediatric Hematology & Oncology		
Protocol:	NOR-GRASPALL 2016		
Document Version No.:	2.0	Document Date:	14-May-2021

The actual value and change from baseline on each study evaluation will be summarized for each clinical laboratory parameter. Baseline is defined as the last value taken prior to the date and time of first dose. In the event of repeat values, the last non-missing value per study day/time will be used.

Shift tables will be performed on laboratory abnormalities of the highest NCI CTCAE grade or the worst severity if there is no NCI CTCAE grade. Shifts from baseline will be classified as improved from baseline, no change from baseline, or worsened from baseline.

All laboratory data will be provided in data listings. A subset listing will be presented for all clinically significant abnormal laboratory values. This listing will present all laboratory values for any parameter with at least one clinically significant abnormal value so that a time course for that lab parameter can be presented.

